#### 11.4.4 Multiplicity Consideration

As this is a Phase 2b study, there will be no multiplicity adjustments for the two active treatments or for the multiple endpoints.

#### 11.4.5 Efficacy Analyses

#### 11.4.6 Safety Variables

Adverse events will be coded using the MedDRA dictionary. Frequencies and percentages of subjects with treatment-emergent adverse events (TEAEs), serious TEAEs, and TEAEs causing premature discontinuation will be provided by treatment group. An AE is treatment emergent if it occurs or worsens after the first dose of study treatment. Furthermore, frequencies will be given of subjects with TEAEs by system organ class; by system organ class and preferred term; by system organ class, preferred term and maximal severity; by system organ class and preferred term for treatment-related TEAEs; and by system organ class, preferred term, and study day of onset. Separate summaries will be performed for ocular and non-ocular AEs.

Other safety endpoints including visual acuity, slit-lamp biomicroscopy, dilated fundoscopy, and intraocular pressure will be summarized by treatment group and visit using descriptive statistics. Changes or shifts from baseline will also be summarized where appropriate. For assessments performed by eye, study eye, and fellow eye will be summarized separately.

#### 11.4.7 Interim Analyses

There will be no interim analyses in this study.

### 12 COMPLIANCE WITH GOOD CLINICAL PRACTICES, ETHICAL CONSIDERATIONS, AND ADMINISTRATIVE ISSUES

This study will be conducted in compliance with the protocol, current Good Clinical Practices (GCPs), including the International Conference on Harmonisation (ICH) Guidelines, and in general, consistent with the Declaration of Helsinki. In addition, all applicable local, state, and federal requirements relevant to the use of IP in the countries involved will be adhered to.

#### 12.1 Protection of Human Subjects

#### 12.1.1 Subject Informed Consent

Informed consent/assent must take place before any study specific procedures are initiated. Signed and dated written informed consent must be obtained from each subject and/or from the subject's parent or legal guardian prior to enrollment into the study. If the subject is under the legal age of consent, the consent form must be signed by a legal guardian or as required by state and/or local laws and regulations.

All informed consent forms must be approved for use by the sponsor and receive approval/favorable opinion from an IRB prior to their use. If the consent form requires revision (e.g., due to a protocol amendment or significant new safety information), it is the investigator's responsibility to ensure that the amended informed consent is reviewed and approved by Ora prior to submission to the governing IRB and that it is read, signed and dated by all subjects subsequently enrolled in the study as well as those currently enrolled in the study.

If informed consent is taken under special circumstances (oral informed consent), then the procedures to be followed must be determined by Ora and/or sponsor and provided in writing by Ora and/or sponsor prior to the consent process.

#### 12.1.2 Institutional Review Board (IRB) Approval

This study is to be conducted in accordance with IRB regulations (U.S. 21 CFR Part 56.103). The investigator must obtain appropriate IRB approval before initiating the study and re-approval at least annually.

Only an IRB approved version of the informed consent form will be used.

#### 12.2 Ethical Conduct of the Study

This study will be conducted in accordance with the ethical principles that originated with the Declaration of Helsinki.

#### 12.3 Subject Confidentiality

All personal study subject data collected and processed for the purposes of this study should be maintained by the investigator and his/her staff with adequate precautions as to

ensure that the confidentiality of the data is in accordance with local, state, and federal laws and regulations.

Monitors, auditors and other authorized representatives of Ora, the sponsor, the IRB/IEC approving this study, the FDA, the DHHS, other domestic government agencies, and other foreign regulatory agencies will be granted direct access to the subject's original medical and study records for verification of the data and/or clinical trial procedures. Access to this information will be permitted to the aforementioned individuals to the extent permitted by law.

A report of the results of this study may be published or sent to the appropriate health authorities in any country in which the IP may ultimately be marketed, but the subject's identity will not be disclosed in these documents.

#### 12.4 Documentation

Source documents may include a subject's medical records, hospital charts, clinic charts, the investigator's study subject files, as well as the results of diagnostic tests such as X-rays, laboratory tests, and EKGs. The investigator's copy of the CRFs serves as the investigator's record of a subject's study-related data.

#### 12.4.1 Retention of Documentation

All study related correspondence, subject records, consent forms, record of the distribution and use of all IP, and copies of CRFs should be maintained on file for at least two years after the last approval of a marketing application in an ICH region and until there are no pending or contemplated marketing applications in an ICH region; or until at least two years have elapsed since the formal discontinuation of clinical development of the IP. These documents will be retained for a longer period if required by the applicable regulatory requirements or by an agreement with the sponsor. It is the responsibility of the sponsor to inform the investigator/institution as to when these documents no longer need to be retained.

If the responsible investigator retires, relocates, or for other reasons withdraws from the responsibility of keeping study records, custody must be transferred to a person who will accept the responsibility. The sponsor must be notified in writing of the name and address of the new custodian.

# 12.5 Labeling, Packaging, Storage, Accountability, and Return or Disposal of Investigational Product

#### 12.5.1 Labeling/Packaging

Investigational drug will be packaged and labeled into clinical kits.

### 12.5.2 Storage of Investigational Product

#### 12.5.3 Accountability of Investigational Product

The IP is to only be prescribed by the principal investigator or his/her named sub-investigator(s), and is to only be used in accordance with this protocol. The IP must only be distributed to subjects properly qualified under this protocol to receive IP.

The investigator must keep an accurate accounting of the IP received from the supplier. This includes the amount of IP dispensed to subjects, amount of IP returned to the investigator by the subjects, and the amount returned or disposed upon the completion of the study. A detailed inventory must be completed for the IP.

#### 12.5.4 Return or Disposal of Investigational Product

All IP will be returned to the sponsor or their designee or destroyed at the study site. The return or disposal of IP will be specified in writing.

# 12.6 Recording of Data on Source Documents and Case Reports Forms (CRFs)

The investigator is responsible for ensuring that study data is completely and accurately recorded on each subject's CRF, source document, and all study-related material. All study data should also be attributable, legible, contemporaneous, and original. Recorded datum should only be corrected in a manner that does not obliterate, destroy, or render illegible the previous entry (e.g., by drawing a single line through the incorrect entry and writing the revision next to the corrected data). An individual who has corrected a data entry should make clear who made the correction and when, by adding to the correction his/her initials as well as the date of the correction.

Data entry of all enrolled and randomized subjects will use software that conforms to 21 CFR Part 11 requirements, and will be performed only by staff who have been trained on the system and have access to the system. Data will not be entered for screen failure subjects. An audit trail will be maintained within the electronic system to capture all changes made within the eCRF database. After the end of the study and database lock, compact discs (CDs) containing copies of all applicable subjects' eCRFs will be provided to each Investigator Site to be maintained on file by the Investigator.

### 12.7 Publications

Authorship and manuscript composition will reflect cooperation among all parties involved in the study. Authorship will be established before writing the manuscript

[figure not shown]

# 14 APPENDICES

# APPENDIX 1: SCHEDULE OF VISITS AND MEASUREMENTS

# APPENDIX 2: EXAMINATION PROCEDURES, TESTS, & EVALUATIONS

[figure not shown]

[figure not shown]

[figure not shown]

# **APPENDIX 3: PROTOCOL AMENDMENT SUMMARY**

Not Applicable.

13.8	SANDE Questionnaire	. 23
13.9	Tear Osmolarity	. 24
14.	Safety Analyses	. 24
14.1	Adverse Events	. 24
14.2	? Visual Acuity (ETDRS)	. 26
14.3	Slit-Lamp Biomicroscopy Examination	. 26
14.4	Dilated Fundoscopy Examination	. 27
14.5	i Intraocular Pressure (IOP)	. 27
15.	Interim Analyses	. 27
16.	Optimization Analyses	. 28
17.	Changes from Protocol-Stated Analyses	. 28
18.	Additional Analyses	. 29
19.	Revision History	. 29
20.	Tables	. 29
21.	Listings	.44
22.	Figures	.46

List of Abbreviations

AE	Adverse Event
ANCOVA	Analysis of Covariance
ATC	Anatomical Therapeutic Chemical Classification
BCVA	Best Corrected Visual Acuity
CAE	Controlled Adverse Environment
CI	Confidence Interval
CRF	Case Report Form
CS	Clinically Significant
CSR	Clinical Study Report
DED	Dry Eye Disease
eCRF	Electronic Case Report Form
ESWE	Endpoint-Specific Worst Eye
ETDRS	Early Treatment of Diabetic Retinopathy Study
HIPAA	Health Information Portability and Accountability Act
ICH	International Conference on Harmonisation
IOP	Intraocular Pressure
ITT	Intent-to-Treat
IWRS	Interactive Web Response System
LOCF	Last Observation Carried Forward
logMAR	Logarithm of the Minimum Angle of Resolution
MedDRA	Medical Dictionary for Regulatory Activities
NCS	Not clinically significant
OSDI	Ocular Surface Disease Index
PDF	Portable Document Format
PP	Per Protocol
PT	Preferred Term
RTF	Rich Text Format
SAAS	Software-as-a-Service
SAE	Serious Adverse Event
SANDE	Symptom Assessment in Dry Eye
SAP	Statistical Analysis Plan
SD	Standard Deviation
SDC	Statistics and Data Corporation, Incorporated
SOC	System Organ Class
SOP	Standard Operating Procedure
TEAE	Treatment-Emergent Adverse Event
TE-SAE	Serious Treatment-Emergent Adverse Event
TFBUT	Tear Film Break-Up Time
VA	Visual Acuity
WHO	World Health Organization

1. Introduction

The purpose of this statistical analysis plan (SAP) is to describe the planned analyses and reporting for protocol ADX-102-DED-009, version 1.0 dated 12Dec2017.

This SAP is being written with due consideration of the recommendations outlined in the most recent International Conference on Harmonization (ICH) E9 Guideline entitled Guidance for Industry: Statistical Principles for Clinical Trials and the most recent ICH E3 Guideline, entitled Guidance for Industry: Structure and Content of Clinical Study Reports (CSR).

This SAP describes the data that will be analyzed and the subject characteristics, efficacy, and safety assessments that will be evaluated. This SAP provides details of the specific statistical methods that will be used. The statistical analysis methods presented in this document will supersede the statistical analysis methods described in the clinical protocol. In keeping with the preliminary nature of a Phase 2 study, additional analyses other than the planned analyses described herein may be conducted as adhoc analyses and will be identified in the CSR. The intent of any such analyses would be to better characterize treatment effects and improve the design of a future Phase 3 study.

2. Study Objectives

The study objectives are as stated below:

2.1 Study Variables

In this Phase 2b study there are no primary or secondary endpoints. All endpoints are considered hypothesis-generating and not hypothesis-testing. Efficacy variables and safety variables follow.

2.2 Efficacy Variables

The efficacy variables include the following:

2.3 Safety Variables

The safety variables include the following:

- Visual acuity (VA) (ETDRS [Early Treatment of Diabetic Retinopathy Study])
- Slit-lamp biomicroscopy
- Adverse event (AE) query
- Dilated Fundoscopy
- Intraocular Pressure (IOP)

2.4 Statistical Hypotheses

The following hypotheses will be tested for each dose of reproxalap, each dry eye disease (DED) sign

and symptom,

3. Study Design and Procedures

3.1 General Study Design

This is a Phase 2b, multicenter, randomized, double-masked, vehicle-controlled, parallel-group design with block enrollment. Approximately 300 subjects will be randomly assigned to one of the three

treatment groups (1:1:1) to receive either Reproxalap Ophthalmic Solution (0.1%, 0.25%) or vehicle solution as topical ophthalmic drops administered bilaterally QID.

Study visits will be referred to in all tables and listings as the expected study day corresponding to the visit to enable reviewers to understand the assessment timing without referring to the protocol visit schedule. The following table shows the scheduled study visits, their planned study day (note that there is no Day 0 and that Day 1 corresponds to the day of randomization), and the acceptable visit window for each study visit:

Scheduled Visit	Planned Study Day	Visit Window
Visit 1	Day -14	± 2 Days
Visit 2	Day 1	N/A
Visit 3	Day 15	± 2 Days
Visit 4	Day 29	± 2 Days
Visit 5	Day 57	± 3 Days
Visit 6	Day 85	± 3 Days

3.2 Schedule of Visits and Assessments

The schedule of visits and assessments is provided below.

30/JUL/2018

4. Study Treatments

4.1 Method of Assigning Subjects to Treatment Groups

Before the initiation of study run-in at Visit 1, each subject who provides written and informed consent will be assigned to a screening number. All screening numbers will be assigned in strict numerical sequence at a site and no numbers will be skipped or omitted. Each subject who meets all the inclusion and none of the exclusion criteria at Visit 1 and Visit 2 will be assigned a randomization number at the end of Visit 2. The Interactive Web Response System (IWRS) will be used to assign all randomization numbers.

Randomization and kit numbers will be assigned automatically to each subject as they are entered into the IWRS. The site staff will dispense kit(s) required until the next visit. The randomization schedule will use block randomization, such that there will be an approximate equal number of subjects assigned to each of the three treatment arms. Both the randomization number and the dispensed study drug kit number(s) will be recorded on the subject's source document and eCRF. The Sponsor, investigators, and study staff will be masked during the randomization process and throughout the study.

4.2 Masking and Unmasking

All subjects, investigators, and study personnel involved with the conduct of the study will be masked with regard to treatment assignments. When medically necessary, the investigator may need to determine what treatment group has been assigned to a subject. When possible (i.e., in non-emergent situations), Ora and/or the study Sponsor should be notified before unmasking study drug. Ora and/or the study Sponsor must be informed immediately about any unmasking event. Unmasked subjects will be discontinued from the study.

5. Sample Size and Power Considerations

The study sample size of 100 per group was selected

6. Data Preparation

Electronic Case Report Forms (eCRF) will be developed by Statistics and Data Corporation, Incorporated (SDC) following SDTM standards unless otherwise specified by Aldeyra Therapeutics, Inc. Data from source documents will be entered into the eCRF by site personnel. All users will complete role-based system and study-specific eCRF training prior to receiving access to the study database. User access will be granted based on a user's role in the study and will be controlled through individual login credentials including a unique User ID and password.

The clinical study database will be developed and tested in **and tested in and tested in and hosted by and tested in a study, and the study, and the study is a state of the tested in a state of the tested in a study is a state of the tested in a study is a state of the tested in a state of tested in**

After data are entered into the clinical study database, electronic edit checks and data review will be performed. All data validation specifications and procedures are detailed in the Data Validation Manual as a separate document. When the database has been declared to be complete and accurate, the database will be locked. Any changes to the database after data have been locked can only be made with the approval of Aldeyra Therapeutics, Inc. and Ora, Inc. in consultation with SDC.

All analyses outlined in this document will be carried out after the following have occurred:

7.1 Intent-to-Treat

The ITT population includes

7.2 Per Protocol

The PP population includes

7.3 Safety

The safety population includes

- 8. General Statistical Considerations
 - 8.1 Unit of Analysis

Safety endpoints will be analyzed

8.2 Missing or Inconclusive Data Handling

Analyses will be performed
8.3 Definition of Baseline
Baseline measures are defined
8.4 Data Analysis Conventions
All data analysis will be performed

30/JUL/2018

8.5 Adjustments for Multiplicity

As this is a Phase 2b study, there will be no multiplicity adjustments for the two active treatments or for the multiple endpoints.

9. Disposition of Subjects

Subject disposition will be presented

10. Demographic and Pretreatment Variables

10.1 Demographic Variables

The demographic variables collected in this study

A subject listing that includes all demographic variables for the ITT population will be provided.

10.2 Pretreatment Variables

Baseline disease characteristics will be summarized

11. Medical History and Concomitant Medications

11.1 Medical History

Medical history will be coded	
Non-ocular medical history will be summarized	

Listings of medical history will be generated separately for ocular and non-ocular data.

11.2 Concomitant Medications

Concomitant medications will be coded	
	Listings of concomitant

medications will be generated separately for ocular and non-ocular data.

12. Dosing Compliance and Treatment Exposure

12.1 Dosing Compliance

Subjects will be instructed on proper use of the subject daily diary and proper instillation and storage of study drug

A subject listing of dosing compliance will also be produced.

12.2 Treatment Exposure

Extent of treatment exposure	
	A such is stilled in a
	A subject listing
of treatment exposure will also be produced.	
13. Efficacy Analyses	
Quantitative efficacy measures collected	

30/JUL/2018

All efficacy measures will also be presented in subject listings.

The following efficacy endpoints will be tested:

Ora Calibra® Ocular Discomfort & 4-Symptom Questionnaire

13.1 Lissamine Green Staining

Corneal and conjunctival lissamine green staining will be performed

30/JUL/2018

13.2 Fluorescein Staining
Corneal and conjunctival fluorescein staining will be performed

13.3 Tear Film Break-Up Time (TFBUT)
TFBUT will be measured

13.4 Unanesthetized Schirmer's Test

Unanesthetized Schirmer's Test will be assessed

13.6 Ora Calibra[®] Ocular Discomfort & 4-Symptom Questionnaire

Ocular discomfort and dry eye symptoms will be assessed

13.6.1 ASSESSMENTS DURING VISITS

Pre-CAE[®], post-CAE[®], change from pre-CAE[®] to post-CAE[®] and changes from baseline in ocular discomfort and dry eye symptoms will be analyzed

13.6.2 DIARY ASSESSMENTS

Each day	subjects will grade the severity
of their dry eye symptoms in their diary	

13.7 Ocular Surface Disease Index[®]

The OSDI [©] will be assessed

13.8 SANDE Questionnaire

The SANDE Questionnaire will be used

30/JUL/2018

13.9 Tear Osmolarity
Tear osmolarity will be measured

14. Safety Analyses

All safety analyses will be conducted using the safety population.

14.1 Adverse Events

An AE is defined as any untoward medical occurrence associated with the use of an IP in humans, whether or not considered IP-related. An AE can be any unfavorable and unintended sign (e.g., an abnormal laboratory finding), symptom, or disease temporally associated with the use of an IP, without any judgment about causality. Exacerbation of conditions related to the signs and symptoms of Dry Eye will not be reported as an AE. The AE reporting period ends upon study exit. Study drug includes the investigational drug under evaluation. All AEs will be coded using MedDRA Version 20.0.

Treatment-emergent adverse events (TEAEs) are defined as any adverse event that occurs or worsens after the first dose of study treatment. AEs recorded in the eCRF which began prior to treatment will not be included in the summary tables but will be included in the AE data listings.

An overall summary will be presented that includes the number of AEs, TEAEs, serious AEs (SAE), and serious TEAEs (TE-SAE). The summary will also include the number and percentage of subjects withdrawn due to an AE, the number and percentage of subjects with an AE resulting in death, and the number and percentage of subjects who experienced at least one AE, TEAE, SAE and TE-SAE, by treatment group and for all subjects. This summary will include breakdowns of AEs further categorized as ocular or non-ocular.

Additional summaries of TEAEs will be provided showing the number and percentage of subjects who experienced at least one TEAE. These summaries will be presented by SOC and PT. Non-ocular TEAEs will be summarized using discrete summary statistics and presented by treatment group at the subject and event level by SOC and PT. Ocular TEAEs will be similarly summarized at the subject and event level. If a subject reports the same PT multiple times within the same SOC, that PT will only be reported once within that SOC. As with the PT, if a subject reports multiple conditions within the same SOC, that SOC will only be reported once. In the summary, SOC will be listed in order of descending frequency for all subjects; PTs will be listed in order of descending frequency for all subjects within each SOC. The occurrence of non-ocular and ocular TEAEs will also be tabulated by SOC, PT, and maximal severity, and by SOC, PT, and study day of onset.

Separate summaries will be provided for the following categories of AEs:

- Ocular TEAEs
- Non-ocular TEAEs
- Treatment-related TEAEs
- SAEs

Severity of an AE is defined as a qualitative assessment of the degree of intensity of an adverse event as determined by the investigator or reported to him/her by the patient/subject. The assessment of severity is made irrespective of relationship to study drug or seriousness of the event and should be evaluated according to the following scale:

- *Mild*: Event is noticeable to the subject, but is easily tolerated and does not interfere with the subject's daily activities.
- *Moderate*: Event is bothersome, possibly requiring additional therapy, and may interfere with the subject's daily activities.
- *Severe*: Event is intolerable, necessitates additional therapy or alteration of therapy, and interferes with the subject's daily activities.

Summaries of TEAEs by maximal severity will be presented for ocular AEs and non-ocular AEs separately. The number of subjects with any TEAEs (along with percentages) will be tabulated by SOC

and PT within each SOC by treatment group. To count the number of subjects with any TEAEs, if a subject has multiple TEAEs coded to the same PT within the same SOC, the subject will be counted once under the maximal severity.

The relationship of each adverse event to the investigational product should be determined by the investigator (in a blinded manner) using these descriptions:

- Definitely Related
- Probably Related
- Possibly Related
- Unlikely to be Related
- Not Related

Definitely related, probably related, and possibly related TEAEs will be considered as treatmentrelated TEAEs. Any TEAEs with missing relationships will also be considered as treatment-related.

All AEs will be presented in a subject listing that classifies each AE as ocular or non-ocular and indicates whether it is a TEAE. Separate listings will be produced for AEs leading to study discontinuation, AEs leading to death and SAEs.

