TABLE 14.2.41	TEAR OSMOLARITY	ITT WITH
		OBSERVED
		DATA ONLY
TABLE 14.3.1.1	ADVERSE EVENT SUMMARY	SAFETY
TABLE 14.3.1.2	ALL OCULAR ADVERSE EVENTS	SAFETY
TABLE 14.3.1.3	ALL NON-OCULAR ADVERSE EVENTS	SAFETY
TABLE 14.3.1.4	ALL OCULAR TREATMENT-EMERGENT ADVERSE EVENTS	SAFETY
TABLE 14.3.1.5	ALL NON-OCULAR TREATMENT-EMERGENT ADVERSE	SAFETY
	EVENTS	
TABLE 14.3.1.6	ALL TREATMENT-RELATED TREATMENT-EMERGENT	SAFETY
	ADVERSE EVENTS	
TABLE 14.3.1.7	ALL SERIOUS ADVERSE EVENTS	SAFETY
TABLE 14.3.1.8	ALL OCULAR TREATMENT-EMERGENT ADVERSE EVENTS	SAFETY
	BY MAXIMAL SEVERITY	
TABLE 14.3.1.9	ALL NON-OCULAR TREATMENT-EMERGENT ADVERSE	SAFETY
	EVENTS BY MAXIMAL SEVERITY	
TABLE 14.3.1.10	ALL OCULAR TREATMENT-EMERGENT ADVERSE EVENTS	SAFETY
	BY STUDY DAY OF ONSET	

Table Number	Title	Population
TABLE 14.3.1.11	ALL NON-OCULAR TREATMENT-EMERGENT ADVERSE	SAFETY
	EVENTS BY STUDY DAY OF ONSET	
TABLE 14.3.2	BEST CORRECTED VISUAL ACUITY	SAFETY
TABLE 14.3.3.1	SLIT LAMP BIOMICROSCOPY	SAFETY
TABLE 14.3.3.2	SHIFT IN SLIT LAMP BIOMICROSCOPY	SAFETY
TABLE 14.3.4.1	DILATED FUNDOSCOPY	SAFETY
TABLE 14.3.4.2	SHIFT IN DILATED FUNDOSCOPY	SAFETY
TABLE 14.3.5	INTRAOCULAR PRESSURE	SAFETY
TABLE 14.3.6	COMPLIANCE WITH STUDY DRUG	SAFETY
TABLE 14.3.7	EXPOSURE TO STUDY DRUG	SAFETY

21. Listings

Listing Number	Title
LISTING 16.1.7	RANDOMIZATION SCHEDULE
LISTING 16.2.1	SUBJECT DISPOSITION
LISTING 16.2.2	PROTOCOL DEVIATIONS
LISTING 16.2.3	STUDY POPULATION INCLUSION
LISTING 16.2.4.1	DEMOGRAPHICS
LISTING 16.2.4.2	OCULAR MEDICAL HISTORY
LISTING 16.2.4.3	NON-OCULAR MEDICAL HISTORY
LISTING 16.2.4.4	PRIOR AND CONCOMITANT OCULAR MEDICATIONS
LISTING 16.2.4.5	PRIOR AND CONCOMITANT NON-OCULAR MEDICATIONS
LISTING 16.2.5.1	IN-OFFICE INSTILLATION
LISTING 16.2.5.2	STUDY DRUG EXPOSURE AND DOSING COMPLIANCE
LISTING 16.2.5.3	STUDY DRUG ACCOUNTABILITY

30/JUL/2018

Listing Number	Title
LISTING 16.2.5.4	URINE PREGNANCY TEST
LISTING 16.2.6.1	LISSAMINE GREEN CORNEAL AND CONJUNCTIVAL STAINING (ORA CALIBRA® SCALE)
LISTING 16.2.6.2	FLUORESCEIN CORNEAL AND CONJUNCTIVAL STAINING (ORA CALIBRA® SCALE)
LISTING 16.2.6.3	TEAR FILM BREAK-UP TIME (TFBUT)
LISTING 16.2.6.4	UNANESTHETIZED SCHIRMER'S TEST
LISTING 16.2.6.5	ORA CALIBRA® OCULAR DISCOMFORT SCALE
LISTING 16.2.6.6	ORA CALIBRA® OCULAR DISCOMFORT & 4-SYMPTOM QUESTIONNAIRE
LISTING 16.2.6.7	STUDY MEDICATION INSTILLATION AND DRY EYE SYMPTOMS REPORTED IN THE SUBJECT DIARY
LISTING 16.2.6.8	OCULAR SURFACE DISEASE INDEX (OSDI)®
LISTING 16.2.6.9	SANDE QUESTIONNAIRE

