LISTING 16.2.6.10	TEAR OSMOLARITY
LISTING 16.2.7.1	ALL ADVERSE EVENTS
LISTING 16.2.7.2	SERIOUS ADVERSE EVENTS
LISTING 16.2.7.3	ADVERSE EVENTS LEADING TO TREATMENT DISCONTINUATION
LISTING 16.2.7.4	ADVERSE EVENTS LEADING TO DEATH
LISTING 16.2.8.1	BEST CORRECTED VISUAL ACUITY - LOGMAR
LISTING 16.2.8.2	SLIT LAMP BIOMICROSCOPY
LISTING 16.2.8.3	DILATED FUNDOSCOPY
LISTING 16.2.8.4	INTRAOCULAR PRESSURE (IOP)

22. Figures

Figure Number	Title	Population
FIGURE 14.2.1	INFERIOR AND TOTAL SUM LISSAMINE GREEN STAINING (ORA CALIBRA® SCALE)	ITT WITH LOCF
FIGURE 14.2.2	INFERIOR AND TOTAL SUM FLUORESCEIN STAINING (ORA CALIBRA® SCALE)	ITT WITH LOCF
FIGURE 14.2.3	OCULAR DISCOMFORT & 4-SYMPTOM QUESTIONNAIRE	ITT WITH LOCF
FIGURE 14.2.4	OCULAR DISCOMFORT & 4-SYMPTOM QUESTIONNAIRE	ITT WITH LOCF

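### SAP 14.1 counts an adverse event that worsens after dosing as treatment-emergent, then excludes it from the summary tables because it began before dosing

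*SAP*

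**What the plan says.** Three statements in SAP 14.1 matter here.

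- The definition: "Treatment-emergent adverse events (TEAEs) are defined as any adverse event that occurs or worsens after the first dose of study treatment".
- The exclusion, in the very next sentence: "AEs recorded in the eCRF which began prior to treatment will not be included in the summary tables". Such events are kept for the listings.
- The listing rule, at the end of the section: "All AEs will be presented in a subject listing that classifies each AE as ocular or non-ocular and indicates whether it is a TEAE".

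The tables that depend on the definition are introduced with: "Additional summaries of TEAEs will be provided showing the number and percentage of subjects who experienced at least one TEAE". The same section plans an overall summary that counts AEs and TEAEs separately. The table list in SAP Section 20 also keeps the two apart: Table 14.3.1.2 is titled "ALL OCULAR ADVERSE EVENTS" and Table 14.3.1.4 "ALL OCULAR TREATMENT-EMERGENT ADVERSE EVENTS".

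Protocol 11.4.6 defines treatment emergence in the same way as the SAP but has no onset-based exclusion. It cannot settle the matter, because the SAP Introduction gives the SAP's methods precedence over the protocol's.

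**The concern.** The worsening limb of the definition exists to capture events already present before dosing. The exclusion removes exactly those events from the tables when the worsening stays on the original record.

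Two programmers could each follow a sentence of SAP 14.1 faithfully and produce different TEAE counts from the same data. The tables would also disagree with the TEAE flag in Listing 16.2.7.1 ("ALL ADVERSE EVENTS") for the same event. Safety and tolerability is one of the three study objectives (Protocol Section 3), so the numerator of the TEAE rate should have a single definition.

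**Working it through.** The plan states no figure to reproduce, so the check is one of logic followed by a count of tables.

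**Can the case arise?** Protocol 10.3 collects AEs from consent onwards. The synopsis places a vehicle run-in of 14 ± 2 days, that is 12 to 16 days, before Visit 2. The visible visit procedures show 3 AE queries before the first randomised dose: two at Visit 1 and one at Visit 2. Events with pre-dose onset will therefore be on file.

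**The three cases**, taking the first dose of study treatment to be the first randomised dose at Visit 2:

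| Onset | Worsens after first dose? | Definition | Exclusion sentence | Result |
|---|---|---|---|---|
| After first dose | not relevant | TEAE | does not apply | consistent |
| Before first dose | no | not a TEAE | excluded | consistent |
| Before first dose | yes, same record | TEAE | excluded | contradiction |

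In set terms, let A be all AEs, P those that began before treatment, and W the part of P that worsened after the first dose on the same record.

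- By the definition: TEAE = (A − P) + W.
- After the exclusion, the TEAE tables show A − P.
- The difference is W, and all of W is lost.

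**How many tables does this reach?** Section 20 of the SAP lists 11 AE tables, 14.3.1.1 to 14.3.1.11. The TEAE-only tables are:

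- ocular: 14.3.1.4, 14.3.1.8 and 14.3.1.10, which is 3;
- non-ocular: 14.3.1.5, 14.3.1.9 and 14.3.1.11, which is 3;
- treatment-related: 14.3.1.6, which is 1.

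The total is 3 + 3 + 1 = 7.

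*Narrow reading (the exclusion covers TEAE summaries only).* These 7 tables plus the TEAE and serious-TEAE rows of 14.3.1.1 give 7 + 1 = 8 of 11. The other 11 − 8 = 3 tables (14.3.1.2, 14.3.1.3 and 14.3.1.7) are untouched. One worsened event is missing from 3 TEAE-only tables (SOC/PT, severity and onset day for its ocular or non-ocular class), or 4 if treatment-related. With 14.3.1.1 that makes 4 or 5 tables.

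*Broad reading (the exclusion covers every AE table).* All 11 are reached. The all-AE tables then also show A − P, so 14.3.1.2 would repeat 14.3.1.4 and 14.3.1.3 would repeat 14.3.1.5. The event is also lost from its all-AE table, and from 14.3.1.7 if serious.

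W is lost from the TEAE tables under both readings.

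**Size.** The documents give no rate of pre-dose AEs or of later worsening, so the number of subjects in W cannot be computed. As an illustration only: with 0 to 3 subjects per arm of 100 whose sole TEAE is of this kind, the any-TEAE rate falls by 0/100 to 3/100, or 0 to 3 percentage points.

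**The case against.** The strongest reply is that the exclusion sentence directly follows the definition and reads naturally as its complement: events that are not treatment-emergent go to the listings only. The affected tables are titled treatment-emergent or count TEAEs, and the protocol uses the same definition. This is probably what was meant, and the duplicated tables under the broad reading support it. But the wording selects on onset, and a programmer who filters on onset date would be doing what the SAP says.

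Second, Protocol 10.1 treats a clinically relevant deterioration in a clinical finding as an AE that has to be recorded. If sites enter the worsening as a new record with its own onset date, it is tabulated and the conflict disappears in practice. That is a real mitigation. However, no visible rule requires a new record or a new onset date when an existing AE worsens.

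Third, SAP 8.3, 8.4 and most of Section 17 are blacked out in the public copy, and a derivation rule could sit there. This limits what can be said about whether the conflict is resolved elsewhere. It does not change the two sentences, which are both fully legible.

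Fourth, the consequence is modest. The table counts show reach, not impact, and would be the same with no such event. Dry-eye exacerbations are not reported as AEs, which removes an obvious source of worsening. New-onset events are unaffected, every event stays in the listings, and no efficacy result, sample size or error rate is involved. All of this stands. It bears on the weight of the point, not on its correctness.

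**Conclusion.** The point holds. Followed exactly, SAP 14.1 drops from the TEAE tables events that its own definition counts, and the tables then disagree with the listing flag. The textual conflict is certain; its numerical effect is unknown and probably small, because the event must begin in a window of about two weeks and worsen later. No direction of bias between arms can be shown.

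The conclusion rests on two conditions: the worsening is kept on the original AE record, and nothing in the redacted sections supplies an exception. It also takes the first randomised dose at Visit 2 as the start of treatment. If the run-in vehicle counted as treatment, the window would shrink but the two sentences would still conflict. The correction should be made, as a clarification of the safety tabulation rules.

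**What to change.** Replace the exclusion sentence in SAP 14.1 with wording such as: *Events with onset before the first randomised dose at Visit 2 that did not worsen after that dose are left out of the TEAE summaries; they stay in the all-AE counts and tables and in the listings.* This closes the contradiction, fixes which dose starts the clock, and settles which tables the exclusion covers.

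Two further specifications are secondary but useful:

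- how worsening is identified from the data actually collected (a rise in severity grade is one option);
- which onset day a worsened event takes in Tables 14.3.1.10 and 14.3.1.11.

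The fields listed in Protocol 10.1 include onset date, end date and severity, but no date of worsening. If the eCRF does not capture one, the SAP needs one more line on how it is derived.

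The cost is one replaced sentence, one derivation flag and possibly that extra line. The table list does not change. TEAE counts may rise slightly in any arm.
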